6.2.9. Usage of Rescue Medication

Usage of rescue medication (incidence, and number of days of usage) during Weeks 1, 2, 4, 8, 12, 16, 24, 32, 40, 48, 56 and 64.

Incidence of rescue medication use will be summarized up to Week 64 using observed data and LOCF imputation. Imputation of weekly diary data after week 56 will not be performed. Number and percentage of subjects taking rescue medication will be shown.

The rescue medication data will be converted to Weekly scores for the week prior to the timepoint of interest. Calculation of the endpoints for both the IPAP and the concomitant medication log data collection is described in [Appendix 2.3](#).

The number of days of rescue medication use per week endpoint will be summarized for the Weeks 1, 2, 4, 8, 12, 16, 24, 32, 40, 48, 56 and 64 using observed data and LOCF imputation. Imputation of weekly diary data after week 56 will not be performed. For this analysis, Baseline data will not be carried forward in the case of a post-Baseline observation not being available for use in LOCF. Number of subjects, mean, median, standard deviation, minimum and maximum will be shown.

Usage of rescue medication (amount taken) during Weeks 1, 2, 4, 8, 12, and 16.

The amount of rescue medication use per week will be summarized for the Weeks 1, 2, 4, 8, 12 and 16 using observed data and LOCF imputation. For this analysis, Baseline data will not be carried forward in the case of a post-Baseline observation not being available for use in LOCF. Number of subjects, mean, median, standard deviation, minimum and maximum will be shown.

6.2.10. Health Care Resource Utilization (HCRU)

HCRU at Baseline, Weeks 64 and 80.

Individual items in HCRU at Baseline, Weeks 64 and 80 will be summarized as described in [Appendix 2.3](#). As for questions obtaining number of visits and number of nights stayed in the hospital, n, mean, median, standard deviation, minimum and maximum will be shown. As for questions obtaining binary or categorical responses, number and percentage of each response category will be shown.

6.2.11. Treatment Satisfaction Questionnaire for Medication v.II (TSQM) Score

TSQM score at Weeks 16 and 56.

The Weeks 16 and 56 responses in the 4 TSQM parameters of satisfaction with effectiveness, side effects and convenience, and overall satisfaction will be summarized.

Summary tables showing number and percentage of patients by value and treatment group will be shown for TSQM items 1-2 and 4-11, and the four satisfaction parameters.

This summary and analysis will use observed data only (no imputation for missing data). The calculation of these endpoints are described in [Appendix 2.3](#).

6.2.12. Patient Reported Treatment Impact Assessment-Modified (mPRTI)

mPRTI at Weeks 16 and 56.

The mPRTI is collected at Weeks 16 and 56. The two endpoints derived from this questionnaire are described below:

- Patient willingness to use drug again. This comes from the question “In the future, would you be willing to use the same drug that you have received in this study for your low back pain?”. This is rated on a 5 point Likert scale from 1 (‘Yes, I would definitely want to use the same drug again’) to 5 (‘No, I definitely would not want to use the same drug again’).
- Patient preference of drug versus prior treatment. This comes from the question “Overall, do you prefer the drug that you received in this study to the treatment you received before this clinical trial?”. This is rated on a 5 point Likert scale from 1 (‘Yes, I definitely prefer the drug I am receiving now’) to 5 (‘No, I definitely prefer my previous treatment’).

Summary tables showing number and percentage of patients by value and treatment group will be shown for all mPRTI questions.

This summary and analysis will use observed data only (no imputation for missing data).

6.3. Other Endpoints: Tertiary Endpoints

6.3.1. Plasma Tanezumab Concentrations

The following reporting of PK data will be done using all available data:

- A listing of all plasma tanezumab concentrations sorted by subject, active treatment group and nominal time post dose. The listing of concentrations will also include the actual times post dose.
- A descriptive summary of the plasma tanezumab concentrations based on nominal time post dose for each treatment group.
- Boxplots of tanezumab plasma trough concentrations at the nominal times for the tanezumab treatment groups.

6.3.2. Serum NGF Assessments

Serum samples from a subset of patients will be run in the bioanalytical assays for assessment of NGF and the measurements will be summarized in the following tables and figures.

- A listing of individual NGF concentrations sorted by subject, active treatment group and time post dose.
- Descriptive statistics of NGF concentrations based on time post dose for each treatment group.
- Boxplots of NGF over time post dose for each treatment group.

6.4. Subset Analyses

Analysis of the data relating to Total Joint Replacement surgery will be performed using the TJR subset analysis set. Reporting of total joint replacement events including surgery and recovery will be described in a separate Statistical Analysis Plan that will cover patients in this subset from Studies 1059, 1061 and 1063. Corresponding data from Studies 1056, 1057 and 1058 will be reported under study 1064. This data from Study 1063 will be reported separately.

6.5. Baseline and Other Summaries and Analyses

6.5.1. Baseline Summaries

The following baseline characteristics will be summarized.

- A summary of baseline characteristics. This summary includes average LBPI, BPI-sf average pain and worst pain, RMDQ total score, PGA-LBP, Low back pain duration and etiology, Quebec Task Force (QTF) category, diabetes status (from medical history and/or pre-treatment HbA1c \geq 6.5%), and pain Detect score ([Appendix 4.3](#)).
- Summaries of Baseline painDetect score in continuous scale (Mean/SD/Min/Max) and by painDetect category (painDetect score \leq 12, 13 to 18, \geq 19).
- Plot of the cumulative distribution function of painDetect score

6.5.2. Study Conduct and Subject Disposition

The following subject dispositions will be summarized.

- Summary of number of patients treated by treatment group.
- Summary table and listing of inclusion and exclusion criteria that are not met by subjects who were screened (but not randomized).
- Summary of time to discontinuation by treatment group and reason, and study week of discontinuation for the treatment period (Weeks 1-2, 3-4, 5-8, 9-12, 13-16, 17-24, 25-32, 33-40, 41-48, 49-56, $>$ 56, total) and for the safety follow-up period (Weeks 1-8, 9-16, 17-24, $>$ 24, total).
- A summary of discontinuation up to End of Treatment period, and up to End of Study period.

6.5.3. Study Treatment Exposure

The following study treatment exposure will be summarized.

- Number of SC doses taken.
- Summary of oral study medication compliance. This is calculated for the interval from Baseline to the entire post-Baseline period up to Week 56 (or end of treatment visit). Compliance is calculated as number of tablets dispensed minus the number returned divided by the number of days in the interval multiplied by 100, to get a percentage compliance for each patient. The number and percentage of subjects in each category (\geq 50%, \geq 80% and \geq 100% compliance) will be shown.

In addition, summary of duration in treatment period and post-treatment follow-up period will be summarized. The number and percentage of patients with each duration category will also be shown. The duration categories are 1-2, 3-4, 5-8, 9-12, 13-16, 17-24, 25-32, 33-40,

41-48, 49-56, >56 for duration in treatment period and 1-8, 9-16, 17-24, >24 for duration in post-treatment follow-up period, respectively.

6.5.4. Concomitant Medications, Non-Drug Treatments and Drug Treatments Prior to Start of Study Treatment

The following concomitant medications and non-drug treatment will be summarized.

- Concomitant drug treatments during the treatment phase through week 64 or up to 16 weeks post the last SC dose will be summarized. Summary of concomitant medications for non-NSAID medication and drug treatments for CLBP, concomitant NSAID medications, concomitant analgesics not used for CLBP, and concomitant non-drug treatments will be shown separately.
- Concomitant drug treatments after 16 weeks post last SC dose will be summarized for analgesics and other treatment for CLBP.
- Number of days of non-study NSAID use per dosing interval (eg, Baseline to Week 8 and Week 8 to Week 16, up to Week 56) and for Week 56 to Week 64. This will show the number and percentage of subjects in a dosing interval who exceeded the limit of 10 days of NSAID use. If a dosing interval exists, the visits will be used to define the interval, otherwise calendar time will be used. A summary of average number of days of NSAID use will be displayed by each interval. Also, a summary of the overall number of days of NSAID use from Day 1 to Week 64 will be shown, as well as the number and percentage of subjects who exceeded the limit of 80 days of NSAID use during this interval.

The treatment prior to start of study treatment will also be summarized. Summary of analgesics and drug treatments for CLBP, analgesics not used for CLBP, non-analgesics and non-CLBP medication, and non drug treatments prior to start of study treatment will be shown separately.

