5.4.1.3. Non-steroidal Anti-inflammatory Drugs (NSAID)

5.4.1.3.1. Celecoxib 100 mg

Celecoxib will be provided as oral capsules containing 100 mg of active celecoxib. Celecoxib 100 mg will be packaged in high-density polyethylene (HDPE) bottles with child resistant closures. The bottles used for the screening period contain 80 capsules (open-label supply) and the bottles used for the treatment period contain 70 capsules (double-blind supply).

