5.4.1.3.2. Placebo to match celecoxib 100 mg

Placebo for celecoxib will be provided as oral capsules matching those used for celecoxib 100 mg capsules. Placebo to match celecoxib 100 mg will be packaged in HDPE bottles with child resistant closures containing 70 capsules (double blind supply).

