5.5.2. Oral Investigational Product Administration

During the Screening period of the study, subjects will be provided with celecoxib and will maintain a stabilized dose regimen of celecoxib 100 mg BID for at least the final 2 weeks (subjects who were receiving celecoxib as pre-study treatment) or 3 weeks (subjects who were receiving loxoprofen or meloxicam as pre-study treatment) of the Screening period

directly prior to the Baseline (Randomization/Day 1) visit. Subjects should be advised to take their morning dose of this celecoxib before arriving for the Randomization/Day 1 clinic visit.

Celecoxib 100 mg or corresponding placebo will be self-administered by subjects orally twice a day (morning and evening) during the double-blind treatment period of the study. On Study Day 1, a morning dose of oral investigational product (celecoxib or corresponding placebo) will not be administered to or taken by subjects. The first dose of oral investigational product will be self administered by subjects on the evening of Day 1. On the days of all other clinic visits (Weeks 2, 4, 8, 16, 24, 32, 40, 48 and 56), subjects should be advised to take their morning dose of celecoxib or corresponding placebo at home prior to the clinic visit.

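### SAP 6.5.3 divides oral capsules taken by days although two are scheduled each day, so full adherence reads about 200%

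*SAP*

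**What the plan says.** SAP 6.5.3 (Study Treatment Exposure) gives the rule for the oral medication: "Compliance is calculated as number of tablets dispensed minus the number returned divided by the number of days in the interval multiplied by 100". The purpose of this step is stated as "to get a percentage compliance for each patient". The interval starts at Baseline and runs "up to Week 56 (or end of treatment visit". Subjects are then counted in three categories: ≥50%, ≥80% and ≥100%.

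The protocol sets the schedule and the unit:

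- **Frequency (5.5.2):** "Celecoxib 100 mg or corresponding placebo will be self-administered by subjects orally twice a day (morning and evening". Table 4 in 5.1 and SAP 2.2 also give twice-daily dosing.
- **Active unit (5.4.1.3.1):** "oral capsules containing 100 mg of active celecoxib".
- **Placebo unit (5.4.1.3.2):** "Placebo for celecoxib will be provided as oral capsules matching those used for celecoxib 100 mg capsules".
- **First dose (5.5.2):** "The first dose of oral investigational product will be self administered by subjects on the evening of Day 1".
- **Later clinic visits, including Week 56 (5.5.2):** "subjects should be advised to take their morning dose of celecoxib or corresponding placebo at home prior to the clinic visit".

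Protocol 5.3 treats 100% as full compliance and asks for counselling when compliance falls below 70% in an 8-week dosing interval.

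**The concern.** The numerator counts capsules and the denominator counts days. The two are on the same scale only at one capsule per day, and all three arms are scheduled two. Nothing in the SAP divides by two, counts scheduled doses, or defines a tablet as a day's supply.

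Celecoxib is the only comparator in the trial, and this table is where a reader would look to see whether it was taken. With the scale doubled, the top category takes in completers who took only slightly more than half their capsules. The error could also go unnoticed. The SAP asks only for counts and percentages in the three categories, with no mean or maximum, so a value near 200% need never appear in the output. The table would simply look like excellent adherence.

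A second gap sits in the same rule. For subjects who stop early, it does not say which date the end of treatment visit refers to. Protocol 9.1 expects 34% to 54% of subjects to complete, so the end date matters for 46% to 66% of them.

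**Working it through.** The documents give no worked compliance value to reproduce, so the check is direct arithmetic on the stated formula.

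**Inputs**

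- Formula: 100 × (dispensed − returned) / days (SAP 6.5.3).
- One capsule per dose, two doses per day, all arms (Protocol 5.1, 5.4.1.3.1, 5.4.1.3.2, 5.5.2).
- One capsule on Day 1 (evening); the morning capsule before the Week 56 visit (Protocol 5.5.2).
- Week 56 on Day 393 (Protocol Table 1): 392 elapsed days, or 393 counted inclusively.
- Early Termination Visit 1 falls 8 weeks after the last SC dose (Protocol 6.9 and 6.9.1.1).

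**Completer.** Scheduled capsules = 1 (Day 1) + 2 × 391 (Days 2 to 392) + 1 (Day 393) = 784 = 2 × 392.

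| True adherence | Capsules taken | Reading, 392 days | Reading, 393 days |
|---|---|---|---|
| 100% | 784 | 200.0% | 199.5% |
| 70% | 548.8 | 140.0% | 139.6% |
| 51% | 399.84 | 102.0% | 101.7% |
| 50% | 392 | 100.0% | 99.7% |

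True adherence needed to reach each SAP category:

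| Category | 392 days | 393 days |
|---|---|---|
| ≥50% | 196/784 = 25.0% | 196.5/784 = 25.1% |
| ≥80% | 313.6/784 = 40.0% | 314.4/784 = 40.1% |
| ≥100% | 392/784 = 50.0% | 393/784 = 50.1% |

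Exact half adherence reaches the top category only on elapsed days; 51% reaches it on either count.

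**Subject stopped at the Week 16 response check.** The last SC dose is on Day 57, so Early Termination Visit 1 also falls on Day 113. Capsules = 2 × 112 = 224, and 224/112 = 200.0%.

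**Other early discontinuers.** Assume the last SC dose on Day 57, the interval run to Early Termination Visit 1 on Day 113, and full adherence until oral dosing stops after the morning dose of Day S. Capsules = 2 × (S − 1), and the reading is 100 × 2 × (S − 1)/112.

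| Oral stop (Day S) | Capsules | Reading to ET Visit 1 |
|---|---|---|
| 58 | 114 | 101.8% |
| 70 | 138 | 123.2% |
| 85 | 168 | 150.0% |
| 113 | 224 | 200.0% |

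If the interval ends when oral dosing stops, each of these subjects reads 200.0%.

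**Check of the remedy.** With scheduled capsules as the denominator, the completer reads 784/784 = 100.0% and the Day 70 stopper 138/138 = 100.0%. Doubling the days without fixing the end date would leave the Day 70 stopper at 138/224 = 61.6%. Doubling inclusive days would put a fully adherent completer at 784/786 = 99.7%, just short of the ≥100% category.

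**The case against.** The case against accepts the completer arithmetic and argues that the point is smaller than it looks.

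- **Reach.** Oral compliance feeds no endpoint, analysis set, imputation rule or model. The analysis sets in SAP 4.1 and 4.2 rest on randomization and SC dosing. This stands, and it limits the point to one descriptive table.
- **Visibility.** A programmer who sees completers near 200% would notice and correct it. That may happen, but the specified output is category counts only, and the SAP is the specification.
- **Early discontinuers.** SAP 5.2.4 ties the end of the treatment period to the Week 56 visit or early discontinuation, and SAP 6.2.8 to that visit or early termination. The protocol places the early-termination visits in follow-up. On that reading every fully adherent subject reads 200% and nothing is mixed. This is a fair reading and perhaps the likelier one. But 6.5.3 names a visit, and some Week 56 assessments move to Early Termination Visit 1 (Protocol Table 2), so the variable figures are a permitted reading and not a demonstrated result.
- **The 70% comparison.** The protocol threshold applies to 8-week intervals at the site, while the SAP figure covers the whole treatment period. That is correct; the 140% reading only illustrates the scale, and the table does not drive the counselling rule.
- **The remedy.** The documents do not show that the timing of the last oral dose (morning or evening) is captured. That is also correct, but it affects one capsule: 1/784 = 0.1% for a completer and 1/138 = 0.7% for the Day 70 stopper.

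**Conclusion.** The formula is wrong as written. For a subject whose interval ends with oral dosing, it overstates adherence by a factor of 2 (1.995 on inclusive days), and the three categories mean about 25%, 40% and 50% of scheduled doses. This rests only on the stated formula, one capsule per dose and twice-daily dosing, all of which are explicit. Actual output would be right only if the programming departed from the text, which the documents do not show.

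The spread from 101.8% to 200.0% among early discontinuers is conditional on ending the interval at Early Termination Visit 1 and on the illustrative dates used. The consequence is a misleading adherence table for the oral comparator and its placebo; no inferential or safety result changes. It should be corrected because the summary cannot be read as labelled and the correction is very cheap.

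**What to change.** Replace the rule in SAP 6.5.3 with: compliance = 100 × (capsules dispensed − capsules returned) / capsules scheduled.

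- Define capsules scheduled as 2 × elapsed days from Day 1 to the Week 56 visit (784 for Day 1 to Day 393).
- For early discontinuers, end the count at the last day of scheduled oral dosing and not at a later early-termination visit (138 for a stop after the Day 70 morning dose). State that this is what the end of treatment visit means in this rule. Doses skipped while oral dosing is still scheduled stay in the denominator.
- Add one capsule if the last scheduled dose is an evening dose. If that timing is not recorded, state the convention used.
- Keep the ≥50%, ≥80% and ≥100% categories.

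The cost is one or two lines of SAP text and one program line. Dispensed and returned counts are already needed for the present formula, and Protocol 5.3 has oral dosing recorded on the CRF, so no new data collection should be needed. No dose or clinical rule changes.

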7. INTERIM ANALYSES

7.1. Introduction

There is no interim analysis for efficacy data planned for this study. The final analysis will be performed after the database is released.

Safety data will be subject to regular and ongoing reporting and review throughout the study. The details of these interim analyses will be documented in a separate Statistical Analysis Plan. Review of the safety data will be by the external Data Monitoring Committee (E-DMC).

7.2. Interim Analyses and Summaries

Events relating to joint safety, including reported Osteonecrosis or events leading to Total Joint Replacement will be reviewed by a blinded expert adjudication panel. A stopping rule relating to a set of adjudicated outcomes has been defined, and is described below.

If the blinded Adjudication Committee identifies adjudicated events of rapidly progressive osteoarthritis type 2, subchondral insufficiency fractures, primary osteonecrosis, or pathological fracture, occurring at a rate that could trigger the protocol-based stopping criteria, an urgent, ad hoc assessment of the events will be made by the E-DMC.

The protocol (or treatment group) stopping rule has three components; the difference in the number of subjects with an adjudicated joint safety event, the exposure-adjusted risk difference (RD) and the exposure adjusted risk ratio (RR) between each tanezumab treatment group and celecoxib treatment group. The exposure-adjusted RD will be calculated as the difference in the ratios of the number of subjects with an adjudicated joint safety event divided by exposure (patient-years) between each tanezumab group and the comparator group. The exposure-adjusted RR will be similarly calculated using the ratio of exposure adjusted event rates (number of subjects with an adjudicated joint safety event divided by exposure) for each tanezumab group relative to the comparator group. The exposure will be calculated as the combined treatment and follow-up periods.

CCI and the RR is and the difference in the number of subjects with adjudicated events joint safety event for any tanezumab treatment group versus the comparator treatment group, the protocol-based stopping rule will be triggered. If the protocol-based stopping rule is triggered, the E-DMC will formulate a recommendation whether it is safe to continue dosing in some or all treatment groups or whether the study should be terminated completely. This decision will be made by Pfizer in consultation with the E-DMC.

Separate sets of dosing suspension rules for specified Serious Adverse Events and events consistent with Hy's Law are described in Sections 9.6.1.1 and 9.6.1.2 of the protocol, respectively.

9. APPENDICES

Appendix 1. SUMMARY OF EFFICACY ANALYSES

Note: BL=Baseline

| Endpoint | Analysis Set | Statistical Method | Model/Covariates | Missing Data | Objective |
|--|--------------|--------------------|---|---------------------|-----------------------------|
| Change from Baseline to Weeks 1, 2, 4, 8, 12, 16, 24, 32, 40, 48, 56 and 64 in aLBPI | ITT | None (summary) | NA | Observed Data | Secondary Endpoint Analysis |
| Change from Baseline to Weeks 16 and 56 in aLBPI | ITT | None (summary) | NA | Multiple imputation | Secondary Endpoint Analysis |
| Change from Baseline to Weeks 16 and 56 in aLBPI | ITT | None (summary) | NA | BOCF | Secondary Endpoint Analysis |
| Change from Baseline to Weeks 16 and 56 in aLBPI | ITT | None (summary) | NA | LOCF | Secondary Endpoint Analysis |
| Change from Baseline to Weeks 1, 2, 4, 8, 12, 16, 24, 32, 40, 48 and 56 in aLBPI | ITT | ANCOVA | BL score, Treatment group (Study site as a random effect) | Multiple imputation | Secondary Endpoint Analysis |
| Change from Baseline to Weeks 2, 4, 8, 16, 24, 32, 40, 48, 56 and 64 in RMDQ total score | ITT | None (summary) | NA | Observed Data | Secondary Endpoint Analysis |
| Change from Baseline to Weeks 16 and 56 in RMDQ total score | ITT | None (summary) | NA | Multiple imputation | Secondary Endpoint Analysis |
| Change from Baseline to Weeks 16 and 56 in RMDQ total score | ITT | None (summary) | NA | BOCF | Secondary Endpoint Analysis |
| Change from Baseline to Weeks 16 and 56 in RMDQ total score | ITT | None (summary) | NA | LOCF | Secondary Endpoint Analysis |

| | | | | | |
|--|-----|----------------|---|---------------------|-----------------------------|
| Change from Baseline to Weeks 2, 4, 8, 16, 24, 32, 40, 48 and 56 in RMDQ total score | ITT | ANCOVA | BL score, BL LBPI score, Treatment group (Study site as a random effect) | Multiple imputation | Secondary Endpoint Analysis |
| Change from Baseline to Weeks 2, 4, 8, 16, 24, 32, 40, 48, 56 and 64 in PGA-LBP | ITT | None (summary) | NA | Observed Data | Secondary Endpoint Analysis |
| Change from Baseline to Weeks 16 and 56 in PGA-LBP | ITT | None (summary) | NA | Multiple imputation | Secondary Endpoint Analysis |
| Change from Baseline to Weeks 16 and 56 in PGA-LBP | ITT | None (summary) | NA | BOCF | Secondary Endpoint Analysis |
| Change from Baseline to Weeks 16 and 56 in PGA-LBP | ITT | None (summary) | NA | LOCF | Secondary Endpoint Analysis |
| Reduction of >0%, ≥10%, to ≥90% (in steps of 10%) and =100% from Baseline to Week 16, 24 and 56 in the aLBPI | ITT | None (summary) | NA | Observed | Secondary Endpoint Analysis |
| Reduction of >0%, ≥10%, to ≥90% (in steps of 10%) and =100% from Baseline to Week 16, 24 and 56 in the aLBPI | ITT | None (summary) | NA | Mixed BOCF/LOCF | Secondary Endpoint Analysis |
| Reduction of >0%, ≥10%, to ≥90% (in steps of 10%) and =100% from Baseline to Week 16, 24 and 56 in the aLBPI | ITT | None (summary) | NA | BOCF | Secondary Endpoint Analysis |
| Reduction of >0%, ≥10%, to ≥90% (in steps of 10%) and =100% from Baseline to Week 16, 24 and 56 in the aLBPI | ITT | None (summary) | NA | LOCF | Secondary Endpoint Analysis |
| Percentage of subjects with reduction of ≥30/50/70/90% from Baseline to Weeks 16, 24, 40 and 56 in the aLBPI | ITT | None (summary) | NA | Observed | Secondary Endpoint Analysis |
| Percentage of subjects with reduction of ≥30/50/70/90% from Baseline to Weeks 16, 24, 40 and 56 in the aLBPI | ITT | None (summary) | NA | Mixed BOCF/LOCF | Secondary Endpoint Analysis |

| | | | | | |
|---|-----|----------------|----|---------------------|-----------------------------|
| Percentage of subjects with reduction of $\geq 30/50/70/90\%$ from Baseline to Weeks 16, 24, 40 and 56 in the aLBPI | ITT | None (summary) | NA | BOCF | Secondary Endpoint Analysis |
| Percentage of subjects with reduction of $\geq 30/50/70/90\%$ from Baseline to Weeks 16, 24, 40 and 56 in the aLBPI | ITT | None (summary) | NA | LOCF | Secondary Endpoint Analysis |
| Percentage of subjects with reduction of $\geq 30/50/70/90\%$ from Baseline to Weeks 16, 24, 40 and 56 in RMDQ total score | ITT | None (summary) | NA | Observed | Secondary Endpoint Analysis |
| Percentage of subjects with reduction of $\geq 30/50/70/90\%$ from Baseline to Weeks 16, 24, 40 and 56 in RMDQ total score | ITT | None (summary) | NA | Mixed BOCF/LOCF | Secondary Endpoint Analysis |
| Percentage of subjects with reduction of $\geq 30/50/70/90\%$ from Baseline to Weeks 16, 24, 40 and 56 in RMDQ total score | ITT | None (summary) | NA | BOCF | Secondary Endpoint Analysis |
| Percentage of subjects with reduction of $\geq 30/50/70/90\%$ from Baseline to Weeks 16, 24, 40 and 56 in RMDQ total score | ITT | None (summary) | NA | LOCF | Secondary Endpoint Analysis |
| Reduction of $>0\%$, $\geq 10\%$, to $\geq 90\%$ (in steps of 10%) and $=100\%$ from Baseline to Week 16 and 56 in RMDQ total score | ITT | None (summary) | NA | Mixed BOCF/LOCF | Secondary Endpoint Analysis |
| Change from Baseline to Weeks 2, 4, 8, 16, 24, 40, 56 and 64 in the BPI-sf Worst Pain | ITT | None (summary) | NA | Observed Data | Secondary Endpoint Analysis |
| Change from Baseline to Weeks 16 and 56 in the BPI-sf Worst Pain | ITT | None (summary) | NA | Multiple imputation | Secondary Endpoint Analysis |
| Change from Baseline to Weeks 16 and 56 in the BPI-sf Worst Pain | ITT | None (summary) | NA | BOCF | Secondary Endpoint Analysis |
| Change from Baseline to Weeks 16 and 56 in the BPI-sf Worst Pain | ITT | None (summary) | NA | LOCF | Secondary Endpoint Analysis |

| | | | | | |
|--|-----|----------------|----|---------------------|-----------------------------|
| Change from Baseline to Weeks 2, 4, 8, 16, 24, 40, 56 and 64 in the BPI-sf Average Pain | ITT | None (summary) | NA | Observed Data | Secondary Endpoint Analysis |
| Change from Baseline to Weeks 16 and 56 in the BPI-sf Average Pain | ITT | None (summary) | NA | Multiple imputation | Secondary Endpoint Analysis |
| Change from Baseline to Weeks 16 and 56 in the BPI-sf Average Pain | ITT | None (summary) | NA | BOCF | Secondary Endpoint Analysis |
| Change from Baseline to Weeks 16 and 56 in the BPI-sf Average Pain | ITT | None (summary) | NA | LOCF | Secondary Endpoint Analysis |
| Change from Baseline to Weeks 2, 4, 8, 16, 24, 40, 56 and 64 in the BPI-sf Pain Interference Index | ITT | None (summary) | NA | Observed Data | Secondary Endpoint Analysis |
| Change from Baseline to Weeks 16 and 56 in the BPI-sf Pain Interference Index | ITT | None (summary) | NA | Multiple imputation | Secondary Endpoint Analysis |
| Change from Baseline to Weeks 16 and 56 in the BPI-sf Pain Interference Index | ITT | None (summary) | NA | BOCF | Secondary Endpoint Analysis |
| Change from Baseline to Weeks 16 and 56 in the BPI-sf Pain Interference Index | ITT | None (summary) | NA | LOCF | Secondary Endpoint Analysis |
| Change from Baseline to Weeks 2, 4, 8, 16, 24, 40, 56 and 64 in the BPI-sf Pain Interference with General Activity | ITT | None (summary) | NA | Observed Data | Secondary Endpoint Analysis |
| Change from Baseline to Weeks 16 and 56 in the BPI-sf Pain Interference with General Activity | ITT | None (summary) | NA | Multiple imputation | Secondary Endpoint Analysis |
| Change from Baseline to Weeks 16 and 56 in the BPI-sf Pain Interference with General Activity | ITT | None (summary) | NA | BOCF | Secondary Endpoint Analysis |
| Change from Baseline to Weeks 16 and 56 in the BPI-sf Pain Interference with General Activity | ITT | None (summary) | NA | LOCF | Secondary Endpoint Analysis |

| | | | | | |
|---|-----|----------------|----|---------------------|-----------------------------|
| Change from Baseline to Weeks 2, 4, 8, 16, 24, 40, 56 and 64 in the BPI-sf Pain Interference with Walking Ability | ITT | None (summary) | NA | Observed Data | Secondary Endpoint Analysis |
| Change from Baseline to Weeks 16 and 56 in the BPI-sf Pain Interference with Walking Ability | ITT | None (summary) | NA | Multiple imputation | Secondary Endpoint Analysis |
| Change from Baseline to Weeks 16 and 56 in the BPI-sf Pain Interference with Walking Ability | ITT | None (summary) | NA | BOCF | Secondary Endpoint Analysis |
| Change from Baseline to Weeks 16 and 56 in the BPI-sf Pain Interference with Walking Ability | ITT | None (summary) | NA | LOCF | Secondary Endpoint Analysis |
| Change from Baseline to Weeks 2, 4, 8, 16, 24, 40, 56 and 64 in the BPI-sf Pain Interference with Sleep | ITT | None (summary) | NA | Observed Data | Secondary Endpoint Analysis |
| Change from Baseline to Weeks 16 and 56 in the BPI-sf Pain Interference with Sleep | ITT | None (summary) | NA | Multiple imputation | Secondary Endpoint Analysis |
| Change from Baseline to Weeks 16 and 56 in the BPI-sf Pain Interference with Sleep | ITT | None (summary) | NA | BOCF | Secondary Endpoint Analysis |
| Change from Baseline to Weeks 16 and 56 in the BPI-sf Pain Interference with Sleep | ITT | None (summary) | NA | LOCF | Secondary Endpoint Analysis |
| Change from Baseline to Weeks 2, 4, 8, 16, 24, 40, 56 and 64 in the BPI-sf Pain Interference with Normal Work | ITT | None (summary) | NA | Observed Data | Secondary Endpoint Analysis |
| Change from Baseline to Weeks 16 and 56 in the BPI-sf Pain Interference with Normal Work | ITT | None (summary) | NA | Multiple imputation | Secondary Endpoint Analysis |

| | | | | | |
|--|-----|----------------|----|-----------------|-----------------------------|
| Change from Baseline to Weeks 16 and 56 in the BPI-sf Pain Interference with Normal Work | ITT | None (summary) | NA | BOCF | Secondary Endpoint Analysis |
| Change from Baseline to Weeks 16 and 56 in the BPI-sf Pain Interference with Normal Work | ITT | None (summary) | NA | LOCF | Secondary Endpoint Analysis |
| The CLBP-RI response at Weeks 16, 24, 40 and 56 | ITT | None (summary) | NA | Observed | Secondary Endpoint Analysis |
| The CLBP-RI response at Weeks 16, 24, 40 and 56 | ITT | None (summary) | NA | Mixed BOCF/LOCF | Secondary Endpoint Analysis |
| The CLBP-RI response at Weeks 16, 24, 40 and 56 | ITT | None (summary) | NA | BOCF | Secondary Endpoint Analysis |
| The CLBP-RI response at Weeks 16, 24, 40 and 56 | ITT | None (summary) | NA | LOCF | Secondary Endpoint Analysis |
| Percentage of subjects with an improvement of ≥ 2 points from Baseline to Weeks 16, 24, 40 56 in the PGA-LBP | ITT | None (summary) | NA | Observed | Secondary Endpoint Analysis |
| Percentage of subjects with an improvement of ≥ 2 points from Baseline to Weeks 16, 24, 40 56 in the PGA-LBP | ITT | None (summary) | NA | Mixed BOCF/LOCF | Secondary Endpoint Analysis |
| Percentage of subjects with an improvement of ≥ 2 points from Baseline to Weeks 16, 24, 40 56 in the PGA-LBP | ITT | None (summary) | NA | BOCF | Secondary Endpoint Analysis |
| Percentage of subjects with an improvement of ≥ 2 points from Baseline to Weeks 16, 24, 40 56 in the PGA-LBP | ITT | None (summary) | NA | LOCF | Secondary Endpoint Analysis |
| Percentage of subjects with any improvement (change <0), no change (change=0), any worsening (change >0) in the PGA-LBP at Weeks 16, 24, 40 and 56 | ITT | None (summary) | NA | Observed | Secondary Endpoint Analysis |

| | | | | | |
|--|-----|----------------|----|-----------------|-----------------------------|
| Percentage of subjects with any improvement (change<0), no change (change=0), any worsening (change>0) in the PGA-LBP at Weeks 16, 24, 40 and 56 | ITT | None (summary) | NA | Mixed BOCF/LOCF | Secondary Endpoint Analysis |
| Percentage of subjects with any improvement (change<0), no change (change=0), any worsening (change>0) in the PGA-LBP at Weeks 16, 24, 40 and 56 | ITT | None (summary) | NA | BOCF | Secondary Endpoint Analysis |
| Percentage of subjects with any improvement (change<0), no change (change=0), any worsening (change>0) in the PGA-LBP at Weeks 16, 24, 40 and 56 | ITT | None (summary) | NA | LOCF | Secondary Endpoint Analysis |
| Time to discontinuation due to lack of efficacy (up to Week 56/End of Treatment) | ITT | KM estimates | NA | Observed Data | Secondary Endpoint Analysis |
| Incidence of rescue medication use during Weeks 1, 2, 4, 8, 12, 16, 24, 32, 40, 48, 56 and 64 | ITT | None (summary) | NA | Observed Data | Secondary Endpoint Analysis |
| Number of days of rescue medication use during Weeks 1, 2, 4, 8, 12, 16, 24, 32, 40, 48, 56 and 64 | ITT | None (summary) | NA | Observed Data | Secondary Endpoint Analysis |
| Amount (mg) of rescue medication taken during Weeks 1, 2, 4, 8, 12, 16 | ITT | None (summary) | NA | Observed Data | Secondary Endpoint Analysis |
| Incidence of rescue medication use during Weeks 1, 2, 4, 8, 12, 16, 24, 32, 40, 48 and 56 | ITT | None (summary) | NA | LOCF | Secondary Endpoint Analysis |
| Number of days of rescue medication use during Weeks 1, 2, 4, 8, 12, 16, 24, 32, 40, 48 and 56 | ITT | None (summary) | NA | LOCF | Secondary Endpoint Analysis |

| | | | | | |
|--|-----|---------------------|----|---------------|-----------------------------|
| Amount (mg) of rescue medication taken during Weeks 1, 2, 4, 8, 12, 16 | ITT | None (summary) | NA | LOCF | Secondary Endpoint Analysis |
| Change from Baseline to Weeks 16, 56 and 64 in WPAI Impairment scores (Percent work time missed due to Low Back Pain; Percent impairment while working due to Low Back Pain; Percent overall work impairment due to Low Back Pain; Percent activity impairment due to Low Back Pain) | ITT | None (summary) | NA | Observed Data | Secondary Endpoint Analysis |
| EQ-5D dimensions (Mobility; Self-care; Usual activity; Pain/Discomfort; Anxiety/Depression) and Overall Health Utility at Baseline and Weeks 16 and 56 | ITT | Summary | NA | Observed Data | Secondary Endpoint Analysis |
| EQ-VAS at Baseline and Weeks 16 and 56 | ITT | Summary | NA | Observed Data | Secondary Endpoint Analysis |
| mPRTI endpoints (willingness to re-use; patient preference; patient satisfaction) at Weeks 16 and 56 | ITT | Summary | NA | Observed | Secondary Endpoint Analysis |
| TSQM endpoints (satisfaction with effectiveness, side effects and convenience, and overall satisfaction) at Weeks 16 and 56 | ITT | Summary | NA | Observed | Secondary Endpoint Analysis |
| Healthcare Resource Utilization at baseline, week 64 and 80 | ITT | Descriptive Summary | NA | Observed | Secondary Endpoint Analysis |

